12.3. Assessment period for the administration status of Humira

Time allowance of assessment period with the first administration date of Humira as 1 is as follows:

Assessment period	Time Allowance(Day)
the first administration to Week 4 of administration	1-28
after Week 4 of administration to Month 3 of administration	29-84
after Month 3 of administration to Month 6 of administration	85-182
after Month 6 of administration to Year 1 of administration	183-364
after Year 1 of administration to Year 1 and Month 6 of administration	365-546
after Year 1 and Month 6 of administration to Year 2 of administration	547-728
after Year 2 of administration to Year 2 and Month 6 of administration	729-910
after Year 2 and Month 6 of administration to Year 3 of administration	911-1092
Continued as of Year 3 of administration	1093-, patients with 'continued' checked

12.4. Assessment period for the onset status of adverse reactions

Time allowance of assessment period with the first administration date of Humira as 1 is as follows:

Assessment period	Time Allowance(Day)
the first administration to Week 4 of administration	1-28
after Week 4 of administration to Month 3 of administration	29-84
after Month 3 of administration to Month 6 of administration	85-182
after Month 6 of administration to Year 1 of administration	183-364
after Year 1 of administration to Year 1 and Month 6 of administration	365-546
after Year 1 and Month 6 of administration to Year 2 of administration	547-728

Assessment period	Time Allowance(Day)
after Year 2 of administration to Year 2 and Month 6 of administration	729-910
after Year 2 and Month 6 of administration to Year 3 of administration	911-1092
Year 3 of administration -	1093 -

12.5. Assessment period for the continued administration of Humira

The assessment period with the first administration date of Humira as 1 is as follows:

Assessment period	Day
At the first administration	1
Week 4 of administration	29
Month 3 of administration	85
Month 6 of administration	183
Year 1 of administration	365
Year 1 and Month 6 of administration	547
Year 2 of administration	729
Year 2 and Month 6 of administration	911
Year 3 of administration	1093

13. Charts to be generated (chart No., chart name)

13.1. General

“1.1.1 Case structure chart”

Patients for analysis: registered patients

Analysis objective: to indicate changes in the number of patients

Analysis items: number of sites with registered patients, number of registered patients, number of sites with patients whose survey form has been locked, number of patients whose survey form was locked, number of patients whose survey form was yet to be locked, the breakdown of the reasons for unlocked survey forms, number of patients in the safety analysis group, number of patients excluded from the safety analysis group, the breakdown of reasons for exclusion from the safety analysis group, number of patients in the effectiveness analysis group, number of patients excluded from the effectiveness analysis group, the breakdown of reasons for exclusion from the effectiveness analysis group

“1.1.2 Case structure chart on patients in the effectiveness analysis group”

Patients for analysis: patients in the effectiveness analysis group

Analysis objective: to indicate changes in the number of patients

Analysis items: number of patients in the effectiveness analysis group, number of patients in the CRP analysis group, number of patients in the WPAI analysis group, number of patients in the endoscopy (large intestine) analysis group, and number of patients in the endoscopy (small intestine) analysis group

Note: the definitions of patients in each analysis group are as follows:

Patients in the CRP analysis group: the patients in the effectiveness analysis group whose CRP level was measured after they were started on Humira.

Patients in the WPAI analysis group: the patients in the effectiveness analysis group whose WPAI was measured after they were started on Humira.

Patients in the endoscopy (large intestine) analysis group: the patients in the effectiveness analysis group who underwent endoscopy (large intestine) after they were started on Humira.

Patients in the endoscopy (small intestine) analysis group: the patients in the effectiveness analysis group who underwent endoscopy (small intestine) after they were started on Humira.

“1.2 Number of sites surveyed and number of patients surveyed (patients in the safety analysis group)”

Patients for analysis: patients in the safety analysis group

Analysis objective: to show the number of patients per site

Analysis items: number of sites surveyed, number of patients in the safety analysis group, the mean, the maximum, the minimum of the number of patients in the safety analysis group per site

“1.1.3 Progress in survey forms”

Patients for analysis: patients whose survey form was locked

Analysis objective: to show the number of locked cases for each separate volume per patients whose survey form was locked, patients in the safety analysis group, and patients in the effectiveness analysis group.

Analysis items: locked cases in the 1st separate volume, locked cases in the 2nd separate volume, locked cases in the 3rd separate volume, locked cases in the 4th separate volume, locked cases in the 5th separate volume, locked cases in the 6th separate volume

“1.3 A list of the patients excluded from the safety analysis and the patients excluded from the effectiveness analysis (including the reason for exclusion)”

Patients for analysis: patients whose survey form was locked

Analysis objective: to show the list of patients excluded from each analysis group and the reason for exclusion

Analysis item: The reason for exclusion will be displayed for the patients not in the safety or efficacy

analysis.

If more than one reason for exclusion exists in a patient, display them in a comma-delimited manner.

“1.3.1. Excluded patients (aggregation by reason)”

Patients for analysis: registered patients

Analysis objective: to show a list of the reasons for exclusion in each analysis group regarding all the patients in the analysis group.

Analysis items: case number, patients whose survey form was yet to be locked, patients excluded from the safety analysis group, the reasons for exclusion from the safety analysis (breach of contract: unsigned site/department, breach of contract: unsigned physician, breach of contract: an excess of the number of signed patients, untreated with Humira, administration prior to contract, administration after the contract expires, administration start not in the registration period, breach of registration criteria: deviation of the registration period, breach of registration criteria: not the disease surveyed, breach of registration criteria: malignant tumour, breach of registration criteria: during the administration period of Humira, not confirmed by physician, patients not registered, overlapped patients, safety not assessable, data credibility not confirmed, data credibility not confirmed (breakdown)), patients excluded from the effectiveness analysis, reasons for exclusion from the effectiveness analysis (effectiveness not assessable)

If data credibility cannot be identified and more than one (breakdown) exists in a patient, display them in a comma-delimited manner.

“1.4 A list of patients (adverse event + search flag)”

Patients for analysis: patients whose survey form was locked

Analysis objective: to show a list of background information per patient, adverse events and administration status by using analysis data.

Analysis items: case number, sex, age, body weight, duration of illness, adverse event (presence/absence of adverse event, safety

Patients with adverse events not in the analysis period, SOC code, System Organ Class, PT code, name of disease (MedDRA PT), adverse events reported by physician, onset date, days from the first administration to the onset, seriousness, causality, outcome, outcome confirmation date, days to the outcome confirmation), CDAI effectiveness at the final assessment, administration status of Humira (the first administration date, the final administration date, days of administration, the initial dose, the maximum dose) presence/absence of complication, presence/absence of medical history, hepatitis B virus test (HBs antigen), with/without administration of anti-hepatitis B virus agent, tuberculosis test (Tuberculin test, QuantiFeron test, chest X ray test, thoracic CT scan, other imaging, tuberculosis test) search flags (patients in the safety analysis group, patients in the effectiveness analysis group, death cases, pediatrics, the elderly, pregnant, nursing, liver disorder, renal disorder, patients with hepatitis B viral infection, patients with an infection, patients with malignant tumour,

patients with AAA measured, contraindication)

Note: Follow “12.1 Assessment period for CDAI, WPAI, CRP and non-intestinal conditions” for CDAI effectiveness in the final assessment period.

In addition, display “remission” or “no remission”. Display “unknown” for patients excluded from the effectiveness analysis.

”1.4.1 A list of adverse events”

Patients for analysis: patients whose survey form was locked

Analysis objective: to show a list of adverse events per patient by using analysis data.

Analysis items: case number, sex, age, SOC code, System Organ Class, PT code, name of disease (MedDRA PT), adverse events reported by physician, onset date, days from the first administration date to the onset date, seriousness, causality,

outcome, outcome confirmation date, dates to the outcome, complication, patients in the safety analysis group, the reasons for exclusion from the safety analysis (breach of contract: unsigned site/department, breach of contract: unsigned physician, breach of contract: an excess of the number of signed patients, untreated with Humira, administration prior to contract, administration after the contract expires, administration start not in the registration period, breach of registration criteria: deviation of the registration period, breach of registration criteria:

not the disease surveyed, breach of registration criteria: malignant tumour, breach of registration criteria: during the administration period of Humira, not confirmed by physician, patients not registered, overlapped patients, safety not assessable, data credibility not confirmed, data credibility not confirmed (breakdown)), patients in the effectiveness analysis group, patients who developed adverse events not in the safety analysis period, search flag (death case, pediatrics, the elderly, pregnant, nursing, liver disorder, renal disorder, patients with hepatitis B viral infection, patients with an infection, patients with malignant tumour, patients with AAA measured, contraindication)

If data credibility cannot be identified and more than one (breakdown) exists in a patient, display them in a comma-delimited manner.

”1.4.2 A list of death cases”

Patients for analysis: patients whose survey form was locked

Analysis objective: to show a list of adverse events in death cases by using analysis data.

Analysis items: case number, sex, age, SOC code, System Organ Class, PT code, name of disease (MedDRA PT), adverse events reported by physician, onset date, days from the first administration date to the onset date, seriousness, causality,

outcome, outcome confirmation date, days to the outcome, complication, patients in the safety analysis group, patients in the effectiveness analysis group, patients who developed adverse events not in the safety analysis period, search flag (death case, pediatrics, the elderly, pregnant, nursing,

liver disorder, renal disorder, patients with hepatitis B viral infection, patients with an infection, patients with malignant tumour, patients with AAA measured, contraindication)

“1.4.3 A list of patients aged 18 years or younger”

Patients for analysis: patients whose survey form was locked

Analysis objective: to show a list of patients aged 18 years or younger by using analysis data.

Analysis items: case number, sex, age, height, body weight, BMI, duration of illness, adverse event (SOC code, System Organ Class, PT code, name of disease (MedDRA PT), adverse events reported by physician, onset date, days from the first administration date to the onset date, seriousness, causality, outcome, outcome confirmation date, days to the outcome), administration status of Humira (the first administration date, the final administration date), discontinued/not discontinued, reason for discontinuation, complication (presence/absence of complication, PT code, name of disease (MedDRA PT), medical history (presence/absence of medical history, PT code, name of disease (MedDRA PT)), condition/ medical history of Crohn's disease (anus/perianal region, rectum, stomach/duodenum, colon, jejunum/ileum, others, intestinal complication, non-intestinal complication), prior medications (anti-TNF α drug, aminosalicylic acid drug, corticosteroids, immunosuppressant, antibiotics), CDAI level (at the first administration, Week 4 of administration, Month 3 of administration, Month 6 of administration, Year 1 of administration, Year 1 and Month 6 of administration, Year 2 of administration, Year 2 and Month 6 of administration , Year 3 of administration)

Note: Follow “12.1 Assessment period for CDAI, WPAI, CRP and non-intestinal conditions” for CDAI level.

“1.5 Administration status of Humira (dosage and administration)”

Patients for analysis: patients in the safety analysis group, patients in the effectiveness analysis group

Analysis objective: to show the administration status of Humira

Analysis items: count the number of patients who receive Humira in the process of “1st time: 160mg→2nd time: 80mg →3rd time: 40mg once every two weeks, and no change thereafter” and the number of “other” patients, and calculate the percentage to the target patients. See 10.1 for how to classify the administration process.

“1.6.1 Administration status of Humira (dosing frequency, dose)

Patients for analysis: patients in the safety analysis group, patients in the effectiveness analysis group

Analysis objective: to show the dosing frequency and the distribution status of the total dose

Analysis items: calculate the number of patients per segment defined in “11 How to stratify data”,

summary statistics and the percentage to the number of patients in the analysis groups regarding dosing frequency and the total dose.

“1.6.2 Administration status of Humira (period)”

Patients for analysis: patients in the safety analysis group, patients in the effectiveness analysis group

Analysis objective: to show the distribution status in the administration period.

Analysis item: Calculate the administration dates based on “days to the final administration date of Humira” of “10.1 General” for the administration period. Then, calculate the number of patients per segment which contains the administration dates in each patient and the percentage to the patients in the analysis group in the Time Allowance defined in “12.3 Assessment period for administration status of Humira”. In addition, calculate summary statistics for the number of days for administration.

“1.6.3 Continuation rate of Humira”

Patients for analysis: patients in the safety analysis group

Analysis objective: to show the continuation rate of Humira using the Kaplan-Meier method.

Analysis items: Calculate At Risk, number of discontinued patients, continuation rate and 95% of continuation rate per assessment period.

Generate the Kaplan-Meier curve with the percentage of the number of discontinued patients to At Risk as the continuation rate.

Note: Follow “12.5 Assessment period for the continuation of Humira administration” for the dates of assessment period.

The days are censored at the first administration date of Humira + 1092 in patients who are still registered at Year 3.

Calculate the analysis items using the Kaplan-Meier method.

At Risk should include the number of patients who are exposed to a discontinuation risk.

“1.7 Administration status of Humira (discontinuation of administration)”

Patients for analysis: patients in the safety analysis group

Analysis objective: to show the number of discontinued patients and the breakdown of the reasons for discontinuation.

Analysis items: Calculate the number of patients in the analysis groups, the percentage to the discontinued patients and patients in the analysis groups, patients ‘with’ reason for discontinuation and unknown/not provided and the percentage to the number of discontinued patients, number of patients per “reason for discontinuation” defined in “11 How to stratify data” and the percentage to the number of discontinued patients.

Note: the reasons for discontinuation may be overlapped in calculation.

In addition, if there are no patients applicable to “multiple choices”, do not display the items of “multiple choices”.

“1.7.1 Administration status of Humira (reason for discontinuation other reasons)

Patients for analysis: patients in the safety analysis group

Analysis objective: to show a list in which the reason for discontinuation is ‘others’.

Analysis item: Calculate the number of patients classified into “others “of “reasons for discontinuation” defined in “11 How to stratify data” by classified item of “reasons for discontinuation, other reason”.

“1.7.2 Administration status of Humira (a list of reasons for discontinuation other reasons)”

Patients for analysis: patients in the safety analysis group

Analysis objective: to show a list in which the reason for discontinuation is ‘others’.

Analysis item: Display other reasons per case number for patients classified into “others“ of “reasons for discontinuation” defined in “11 How to stratify data”.

“1.12 Distribution status of patient backgrounds”

Patients for analysis: patients in the safety analysis group, patients in the effectiveness analysis group, patients whose survey form was locked

Analysis objective: to show the distribution status of patient backgrounds

Analysis item: calculate the number of patients in the analysis groups.

Calculate the number of patients per the following segment defined in “11 How to stratify data” and the percentage to the number of patients in the analysis groups.

Sex, pregnancy/nursing, age (year), body weight (kg), BMI (kg/m²), duration of illness (year), indication (registration form), allergy history, smoking history, detailed classification of smoking history, tuberculosis test, hepatitis B virus test status (registration form), complication, detailed classification of complications, complication/others, medical history, detailed classification of medical history, prior medication for Crohn's disease, detailed classification of prior medication for Crohn's disease, prior treatment for Crohn's disease, detailed classification of prior treatment for Crohn's disease, treatment history with anti-TNF α drug for Crohn's disease, reason for discontinuation of treatment history of anti-TNF α drug, concomitant medication, detailed classification of concomitant medications, concomitant treatment for Crohn's disease, detailed classification of concomitant treatment for Crohn's disease, condition/medical history of Crohn's disease (site of disease of condition/medical history of Crohn's disease), intestinal complications of condition/medical history of Crohn's disease, non- intestinal complications of condition/medical history of Crohn's disease), work condition, CDAI when the administration was started, CRP

In addition, calculate summary statistics for the following:

age (year), body weight (kg), BMI (kg/m²), duration of illness (year), CDAI when the administration was started, CRP

Note: for pregnancy/nursing, calculate the percentage to female patients.

Note: For the discontinuation reasons for anti-TNF α drug, calculate the percentage to the patients with treatment history of anti-TNF α drug.

“1.13 Distribution status of self-administration”

Patients for analysis: patients in the safety analysis group

Analysis objective: to show the distribution status regarding presence/absence of self-administration

Analysis item: calculate the number of patients in the analysis groups.

Calculate the number of patients per “self-administration” defined in “11. How to stratify data” and the percentage to the number of patients in the analysis groups.

“1.16 A list of patients with AAA measured

Patients for analysis: patients in the safety analysis group

Analysis objective: to show a list of patients with AAA measured.

Analysis item: display the following items in “patients with AAA measured” defined in “10.1 General”.

Case number, administration status of Humira (the first and final administration dates), concomitant medications, serum anti-adalimumab antibody (blood sampling date, positive/negative) adverse events reported by physician, name of disease (MedDRA PT), System Organ Class, onset date, seriousness, causality, outcome confirmation date, outcome, CDAI remission

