In the event of a serious adverse event, and additionally, any non-serious events of malignancy in patients 30 years of age and younger, whether related to adalimumab or not, if applicable - the physician will notify the AbbVie contact person (Medical Representative in Japan) within 24 hours of the physician becoming aware of the event.

7. Duration of the investigation

Registration period: November 2011 ~ October 2013

Investigation period: November 2011 ~ March 2017

<Milestones>

Major study milestones and their planned dates are as follows:

Start of Data Collection: November 2011

Registration in the EU PAS register: Not Applicable

End of Study: The date on which statistical analysis dataset for

8. Items to be investigated

(1) Observation period

Patients will be observed for 3 years after the initiation of Humira treatment. (Patients who will continue Humira treatment for more than 3 years will also be evaluated at the end of third year to enable completion of the CRF). Patients who have been lost to follow-up during the observation period due to transfer to another hospital, discontinuation of treatment* or for other reasons will be handled as cases of discontinuation of the survey.

* A patient who has suspended Humira treatment for at least 2 months should be considered a case of discontinuation of Humira treatment that will be handled as a case of discontinuation of the survey.

(2) Registration form

Name of institution, date of completion of the registration form, name of department, name of investigator, patient ID, patient's birthdate (year/month) or age, sex, presence/absence of pregnancy/lactation (for female patients), reasons for use of Humira, date (or planned date) of initiation of Humira treatment, contraindications to use of Humira, conditions requiring special care in administration, presence/absence and effectiveness of previous treatment of Crohn's disease, history of biological therapy, presence/absence of tuberculosis or other infection (tuberculin skin test, Quantiferon test, chest X-ray, and chest CT), hepatitis B virus test (HBs antigen test), presence/absence of preventive anti-tuberculosis treatment, and baseline laboratory data (blood β-D-glucan level, peripheral blood WBC, and peripheral blood lymphocyte count).

(3) Data to be collected via CRF

1) Patient background

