13) Discontinuation of the investigation

Reasons for discontinuation of the investigation [occurrence of adverse event (AEs), insufficient response to Humira, patient's request, no visits, others].

14) AEs (including abnormal laboratory findings)

Presence/absence and nature of AEs, date of onset, seriousness, causal relationship with Humira treatment, suspected drugs, clinical course of AEs, measures taken (measures related to Humira treatment and symptomatic treatment), outcome, laboratory findings (indicate laboratory values when abnormal laboratory findings are observed), and reasons for the rating of causal relationships when the investigator concludes that there is no causal relationship.

15) Product Quality Complaints

A Complaint is any written, electronic, or oral communication that alleges deficiencies related to the physical characteristics, identity, quality, purity, potency, durability, reliability, safety, effectiveness, or performance of a product/device after it is released for distribution.

The investigational product in this trial contains both:

-Biologic compound(s) and

-Device component(s) (pre-filled syringe, pen).

• Definition

A Product Complaint is any Complaint related to the biologic or drug component of the product or

to the medical device component(s).

For a product this may include, but is not limited to, damaged/broken product or packaging, product appearance whose color/markings do not match the labeling, labeling discrepancies/inadequacies in the labeling/instructions (example: printing illegible), missing components/product, device not working properly, or packaging issues.

For medical devices, a product complaint also includes all deaths of a patient using the device, any illness, injury, or adverse event in the proximity of the device, an adverse event that could be a result of using the device, any event needing medical or surgical intervention including hospitalization while using the device and use errors.

Any information available to help in the determination of causality by the device to the events outlined directly above should be captured.

- Reporting

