10.1. General

Data name	Derivation and calculation methods
Number of sites for this survey	Aggregate the number with DCF code.
The first administration date of Humira	It shall be the oldest date among the dates described in “the administration status of Humira” in the survey form.
The final administration date of Humira	
Do not use for analysis the record of the first administration date of Humira + 1092 days < the first administration date among the data described in “the administration status of Humira” in the survey form.
 
The final administration date of Humira shall be the most recent date among the final administration dates imputed in the following [1] to [4]:
 
[1] Sort data in the order of “the first administration date” of “the administration status of Humira”, dosing frequency and description.
 
[2] If the final date is provided, there is no check on the checkbox of “continued”, and the final administration date can be identified, select the date described as the final administration date.
 
If the final date is not described, the checkbox of “continued” is checked, and the final administration date cannot be identified, follow the below:
 
 • The final record: Impute the first administration date of Humira + 1092 days on the final administration date. • Other than the final record: Impute the first administration date of the next record - 1 day on the final administration date. 
[3] Even though the final dates are described, but the final administration date is incomplete and cannot be identified, follow the below:
 
 • If the year and month are described but the date is unknown, impute the final date of the month as the final administration date. • If the year is described and the month and date are unknown, impute the final date of the year as the final administration date. If the next record has already been generated and the first administration date of the next record comes earlier than the imputed date, impute the first administration date of the next

Data name	Derivation and calculation methods

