	
record - 1 day for the final administration date.
 
Of note, if the final administration date is provided in the record where the final administration date of Humira has been identified according to the above rule and the “continued” checkbox is checked, follow the below:
 
 ● If the described final administration date > the final administration date imputed according to the above rule, select the imputed final administration date as the final administration date of Humira for the patient. ● If the described final administration date <= the final administration date imputed according to the above rule, select the described final administration date as the final administration date of Humira for the patient. 
If the first administration date of Humira + 1092 days < the final administration date of Humira imputed according to the above rule, select the first administration date of Humira + 1092 days as the final administration date of Humira.

Days to the final administration date of Humira	The final administration date of Humira - the first administration date of Humira + 1
Total exposure period (in years)	(Days to the final administration date of Humira + 28) / 364
Discontinued patients	
 • Patients whose final administration date of Humira comes before the first administration date of Humira + 1064 (Week 152) • Patients with a washout period with 60 days or longer. 
*The final administration date of Humira should be the administration date right before the washout of ≥ 60 days starts.

Reason for discontinuation	When a reason for discontinuation is described in the survey form, it is defined as ‘with’ reason for discontinuation. When no such description is found, it is defined as an “unknown/not provided”.
Death cases	At least a piece of data on “death” is found as the outcome of the adverse events during the safety analysis period.
Pediatrics	Patients aged < 15 years
The elderly	Patients aged ≥ 65 years

Data name	Derivation and calculation methods
Presence/absence of complications	When complication data are contained in the survey form, it should be classified as “with complications”. When the description in the survey form is not clear enough (when the check of with/without complications is not assessable or when multiple checkboxes are checked), it should be ‘unknown’ while no description should be ‘not provided’. Other cases are “no complications”.

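### Chart 1.6.3 has no censoring rule for patients who leave the survey before Year 3 while still on Humira, so how the last form was filled in decides whether they count as stopping or as continuing

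*SAP*

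**What the plan says.** **The chart.** SAP 13.1, chart 1.6.3, covers the safety analysis group: "Analysis objective: to show the continuation rate of Humira using the Kaplan-Meier method". Its only censoring instruction is: "The days are censored at the first administration date of Humira + 1092 in patients who are still registered at Year 3". On the risk set it adds: "At Risk should include the number of patients who are exposed to a discontinuation risk". It does not say when a patient lost to the survey leaves that set.

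**The event.** The chart counts discontinued patients, a term that SAP 10.1 defines by two criteria. The first is "Patients whose final administration date of Humira comes before the first administration date of Humira + 1064 (Week 152", and the second is "Patients with a washout period with 60 days or longer". The reason for leaving plays no part in either.

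**The last-dose date.** This date drives the first criterion. Under SAP 10.1, where the final record has no end date and the 'continued' box "is checked, and the final administration date cannot be identified, follow the below", the last dose is set to first dose + 1092 days. Where 'continued' is ticked and an earlier date is also written, the written date is used.

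**Leaving the survey.** Protocol section 8(1) refers to "Patients who have been lost to follow-up during the observation period due to transfer to another hospital, discontinuation of treatment* or for other reasons" and treats all of these as discontinuation of the survey. Its footnote equates only a suspension of at least 2 months with discontinuation of Humira. Protocol section 8(3), item 13, collects "Reasons for discontinuation of the investigation [occurrence of adverse event (AEs), insufficient response to Humira, patient's request, no visits, others". SAP section 11 uses nearly the same list for chart 1.7, whose title refers to discontinuation of administration. Neither list has a category for leaving while on treatment.

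**The concern.** A patient who changes hospital on stable treatment has not stopped Humira. After the last date known on drug, the patient's status is unknown, and a persistence curve should censor there. The SAP has no such step.

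Take two patients who both transfer on treatment at Month 14. For one, the site writes the last dose given there. That date is before first dose + 1064 days, so the patient is a Kaplan-Meier event and is counted as discontinued in chart 1.7. For the other, the site ticks 'continued' and writes no date. That patient is credited with treatment to Year 3, some 22 months beyond the last observation. Their histories are the same and their outcomes are opposite.

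At stake are the SAP's only time-to-event description of how long patients stay on the drug, and the count and percentage in chart 1.7. Both go into a report on long-term treatment.

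**Working it through.** **1. The plan's own figure.** The documents state no continuation rate. Their only design figure is about 300 patients for a 95% chance of at least one malignant tumour at about 1.0%. It reproduces: ln 0.05 / ln(1 − 0.01) rounds up to 299, and 300 patients give 0.951. Registering 500 leaves a margin of 1 − 300/500 = 40% for all withdrawals and dropouts. That margin is not a rate of leaving while on drug, so it cannot size this problem.

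**2. Outcome by form entry.** For a patient who leaves on drug before first dose + 1064 days, SAP 10.1 and chart 1.6.3 give:

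| Last record | Last-dose date used | Status in chart 1.6.3 | Bias |
|---|---|---|---|
| Date written, 'continued' not ticked | Written date | Event | Downward |
| Date written, 'continued' ticked | Written date, being earlier | Event | Downward |
| No date, 'continued' ticked | First dose + 1092 | At risk to Year 3 | Upward |

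No row leads to censoring at the last date known on drug.

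**3. Illustration.** These inputs are assumptions, not taken from the documents: true 3-year persistence S, share L who leave on drug within 3 years, constant hazards, and leaving unrelated to stopping.

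- Cumulative stopping hazard over 3 years: H_s = −ln S.
- Cumulative leaving hazard H_l solves L = H_l/(H_s + H_l) × [1 − exp(−(H_s + H_l))].
- All leavers are events: chart value = exp(−(H_s + H_l)).
- All leavers are censored at exit: chart value = S.
- All leavers are carried to + 1092: chart value = 1 − H_s/(H_s + H_l) × [1 − exp(−(H_s + H_l))].

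With S = 0.60 and L = 0.10, H_s = 0.5108 and H_l = 0.1358, a total of 0.6466.

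- All events: exp(−0.6466) = 0.524.
- Censored: 0.600.
- All carried: 1 − (0.5108/0.6466) × 0.476 = 0.624.

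Per 500 patients this means about 188 who stop, 50 who leave on drug and 262 still on drug in the survey. The chart then shows 262/500 = 52.4% or (262 + 50)/500 = 62.4%. A simulation of 500 Kaplan-Meier analyses of 500 patients gave means of 52.3%, 59.9% and 62.3% for the three treatments.

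**4. Range.** Each cell shows all events / all carried:

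| True S | L = 5% | L = 10% | L = 20% |
|---|---|---|---|
| 50% | 46.5 / 51.5 | 43.1 / 53.1 | 36.4 / 56.4 |
| 60% | 56.2 / 61.2 | 52.4 / 62.4 | 44.9 / 64.9 |
| 70% | 65.8 / 70.8 | 61.7 / 71.7 | 53.5 / 73.5 |
| 80% | 75.5 / 80.5 | 71.1 / 81.1 | 62.2 / 82.2 |

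The error runs from 3.5 to 17.8 points too low if all are events, and from 0.5 to 6.4 points too high if all are carried.

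**5. Where the errors cancel.** The two extremes differ by L. The chart is therefore unbiased at Year 3 when the share carried is (S − all-events value)/L. At S = 0.60 and L = 0.10 this is (0.600 − 0.524)/0.10 = 0.76. Over the grid it runs from 0.68 to 0.89.

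**6. Chart 1.7.** In the same illustration, if every leaver has a written date, chart 1.7 counts 188 + 50 = 238 discontinued patients (47.6%), against 188 (37.6%) who stopped the drug.

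**The case against.** A reader might infer that the continuation rate is understated. The documents do not support that as a general statement. A patient who moves hospital while on Humira is a natural candidate for a ticked 'continued' box with no end date, and SAP 10.1 then carries that patient to Year 3. Nothing in the documents says how sites completed such records. Under the assumptions above, the net bias is downward unless about 68% to 89% of leavers fall under the 'continued' rule. That share is unknown, so the direction is not established. Possible cancellation does not rescue the chart, because it would be accidental.

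Three further points have weight:

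- The pooling starts in the protocol, which lists transfer and treatment discontinuation together and collects one set of reasons. The SAP inherits it.
- Charts 1.7.1 and 1.7.2 classify and list the 'others' reasons, so a transfer recorded there can be seen. They do not remove it from the discontinued count or from the curve.
- Continuation rate is not among the analysis items in protocol section 9 or SAP 5.1, and no comparison or decision rests on it. That limits the importance of the point but does not make the rule right.

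**Conclusion.** The rule is wrong as written, for a descriptive output. That follows from the text alone: the only censoring is for patients still registered at Year 3, and SAP 10.1 turns earlier on-treatment exits into events or into full follow-up according to the form entry. That chart 1.6.3 counts these exits as events follows from applying the 10.1 definition, since the chart itself does not mention them.

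The size depends on the assumed persistence, the assumed share leaving on drug, constant hazards and independence of leaving from stopping. With 60% persistence and 10% leaving, the chart could show anything from about 52% to 62% for a true 60%. If leaving is related to stopping, censoring is not free of bias either, which is why the unclear cases should be shown both ways.

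**What to change.** In SAP 13.1 and 10.1:

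- **Censor** at the last date known on drug any patient whose recorded reason, including classified 'others' text, is transfer or another exit while on treatment.
- **End the 'continued' imputation** at the last CRF or contact date, with first dose + 1092 kept only as the upper limit. Amend the Week 152 criterion at the same time. Otherwise a patient whose imputed date now falls before first dose + 1064 would become an event.
- **Count as events** all recorded stops of Humira, including those under 'others', and washouts of at least 60 days as the SAP already defines them.
- **Show both ways**, as events and as censored, the 'no visit' cases and those where 'patient's wish' could mean leaving the survey and not stopping the drug.
- **Report** in charts 1.6.3 and 1.7 the number who left the survey on treatment, as a separate row outside the Humira discontinuation percentage.

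The cost is SAP wording and one derived flag from reasons already collected. Some 'others' and 'no visit' cases need a judgement, which should be made under a written rule. The last-dose date in 10.1 also feeds the total exposure period, so the SAP should say whether the new imputation applies there or only to the continuation analysis.
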